8.2 Operational definitions for (S) AEs

An adverse event is any untoward medical occurrence in a subject administered a pharmaceutical product and which does not necessarily have a causal relationship with the study treatments. An adverse event (AE) can therefore be any unfavourable and unintended sign (including an abnormal laboratory finding), symptom, or disease temporally associated with the use of a medicinal (investigational) product, whether or

CONFIDENTIAL

not considered related to the medicinal (investigational) product.

Adverse events observed by the Investigator, or reported by the subject, and any remedial action taken, will be recorded in the subject's CRF and should be verifiable in the subject's notes throughout the study. The nature of each event, time of onset after drug administration, duration and severity will be documented together with the Investigator's opinion of the causal relationship to the investigational product (unrelated, unlikely, possible, probable, and definite).

All subjects experiencing adverse events, whether considered associated with the use of the study medication or not, must be monitored until the symptoms subside and any clinically relevant changes in laboratory values have returned to baseline, or until there is a satisfactory explanation for the changes observed.

Procedures such as surgery should not be reported as adverse events. However, the medical condition for which the procedure was performed should be reported if it meets the definition of an adverse event. For example, an acute appendicitis that begins during the adverse event reporting period should be reported as the adverse event and the resulting appendectomy noted on the CRF.

Planned procedures such as surgery pre planned prior to the subject's enrolment into the study do not need to be reported as adverse events if these are documented as planned at the screening visit.

Clinically significant changes in physical examination and blood safety profiles should also be recorded as adverse events.

8.2.1 Assessment of Intensity

Severity should be recorded and graded according to the AIDS Clinical Trial Group (ACTG) Grading Scale (*appendix 2*).

Note: There is a distinction between the seriousness and the intensity of an adverse event. Severe is a measure of intensity; thus, a severe reaction is not necessarily a serious adverse event. For example, a headache may be severe in intensity but would not be classified as serious unless it meets one of the seriousness criteria for serious events.

All events deemed to be Grade 4 (potentially life threatening) according to the ACTG grading scale should be

CONFIDENTIAL

routinely reported as a serious adverse event. However, there may be occasions where in the investigator's clinical judgement they do not consider the event to be life threatening therefore they do not consider the event to meet the definition of an SAE. In these cases, the investigator must document clearly in the participants source documentation that the Grade 4 event has been assessed and why in their clinical judgement they do not consider the event to be life threatening.

8.2.2 Assessment of Causality

The relationship to study drug of each adverse event will be assessed using the following definitions:

DEFINITE: distinct temporal relationship with drug treatment. Known reaction to agent or chemical group or predicted by known pharmacology. Event cannot be explained by subject's clinical state or other factors.

PROBABLE: reasonable temporal relationship with drug treatment. Likely to be known reaction to agent or chemical group or predicted by known pharmacology. Event cannot easily be explained by subject's clinical state or other factors.

POSSIBLE: reasonable temporal relationship with drug treatment. Event could be explained by subject's clinical state or other factors.

UNLIKELY: poor temporal relationship with drug treatment. Event easily explained by subject's clinical state or other factors.

UNRELATED: the event occurs prior to dosing. Event or intercurrent illness is due wholly to factors other than drug treatment.

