Peripheral Blood Monoclonal Cell (PBMC) Central Laboratory	[name] Institut de Recerca del Sida Irsi Caixa Hospital Germans Trias i Pujol 2nd floor, Maternity building [name]
PK Central Laboratory	[name] Liverpool Bioanalytical Facility Royal Liverpool University Hospital [name]

CONFIDENTIAL

STUDY SYNOPSIS

Full study Title	An open-label, multi-centre, randomised, switch study to evaluate the virological efficacy over 96 weeks of 2-drug therapy with DTG/RPV FDC in antiretroviral treatment-experienced HIV-1 infected subjects virologically suppressed with NNRTIs resistance mutation K103N.
Short title/Acronym	WISARD: acronym of SW itch Study mut A tion Rilpivirine D olutegravir.
Clinical Phase	3b
Trial Design	Open-label, 2 arm, phase 3b, multi-centre switch study
Name of Investigational Product	Dolutegravir & Rilpivirine 2 drug fixed dose combined therapy. "Juluca" is the brand name and will hereinafter be referred to as combined dolutegravir (DTG) and rilpivirine (RPV). Investigational product may be provided as commercial "Juluca" or unbranded supply of DTG + RPV. Boosted protease inhibitors or other ARV regimen (including Anatomical Therapeutic Chemical Classification System codes: JO5AB, JO5AE, JO5AF, JO5AG, JO5AR, JO5AX)
Trial Participants population	≥ 18years, male & female
Planned Sample Size	Up to 150 evaluable subjects.
Eligibility Criteria	HIV-1 infected adults aged 18 years or over, virologically suppressed with NNRTIs resistance mutation K103N. (Subjects who at any time have had the mutations 100I, 101E/P, 106A/M, 138K/G/Q, 181C/I/V, 188L, 190A/S/E/Q, 230L mutations are to be excluded. Other NNRTI region variants can be included).
Treatment duration	96 weeks
Follow up duration	30 days
Formulation, Dose, Route of Administration	Experimental arm (Baseline visit switch group): One combined Dolutegravir 50mg /Rilpivirine 25mg FDC tablet taken orally once daily for 96 weeks. Control arm (deferred week 48 switch group): patients will continue their current boosted PI regimen (or other antiretroviral combination) for 48 weeks. Patients will then be switched to one combined Dolutegravir/Rilpivirine FDC tablet taken orally once daily for 48 weeks.
Indication	HIV-1 infected patients with a history of virological failure to NNRTIs and having the K103N mutation.

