1.1. Assessment and management of risk

Summaries of findings from both clinical and non-clinical studies conducted with DTG or RPV can be found in the IBs and product labels for each individual drug.

The following section outlines the risk assessment and mitigation strategy for DTG and RPV in this protocol. Where available, the approved country product label should be referenced. For other ART regimens the approved country product labels should be referenced. See section 7.2 for RSI details.

CONFIDENTIAL

Table 1.0 : Outline of the risk assessment and mitigation strategy for this protocol

Potential Risk of Clinical Significance	Data/Rationale for Risk	Mitigation Strategy
Investigational Product (IP) [DTG/RPV FDC] Refer to individual IBs for DTG and RPV and the Juluca SmPC for additional information		

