6.13 Liver Chemistry Stopping and Follow up Criteria

Liver chemistry threshold stopping criteria have been designed to assure subject safety and to evaluate liver event etiology during administration of study drug and the follow-up period. Study drug must be stopped if any of the following liver chemistry criteria are met:

- ALT $\geq 3 \times \text{ULN}$ and bilirubin $\geq 2 \times \text{ULN}$ (>35% direct bilirubin; bilirubin fractionation required)

NOTE: serum bilirubin fractionation should be performed if testing is available. If testing is unavailable, record presence of detectable urinary bilirubin on dipstick, indicating

CONFIDENTIAL

direct bilirubin elevations and suggesting liver injury. If testing is unavailable and a subject meets the criterion of total bilirubin ≥ 2 xULN, then the event meets liver stopping criteria and should be reported as an SAE. If INR is obtained, include values on the SAE form. INR elevations >1.5 suggest severe liver injury.

- ALT ≥ 8 xULN;
- ALT ≥ 3 xULN (if baseline ALT is $<$ ULN) with symptoms or worsening of acute hepatitis or hypersensitivity such as fatigue, nausea, vomiting, right upper quadrant pain or tenderness, fever, rash, or eosinophilia, OR;
- ALT ≥ 3 x baseline ALT with symptoms or worsening of acute hepatitis or hypersensitivity such as fatigue, nausea, vomiting, right upper quadrant pain or tenderness, fever, rash, or eosinophilia;
- ALT ≥ 5 xULN and < 8 xULN that persists > 2 weeks (with bilirubin < 2 xULN and no signs or symptoms of acute hepatitis or hypersensitivity);
- ALT ≥ 5 xULN but < 8 xULN and cannot be monitored weekly for > 2 weeks;

Subjects who develop ALT ≥ 5 xULN should be followed weekly until resolution or stabilisation (ALT < 5 xULN on 2 consecutive evaluations).

When liver chemistry stopping criterion is met, the following procedures must be followed:

- **Immediately** hold dolutegravir and rilpivirine. If a causal relationship between the liver event and dolutegravir and rilpivirine cannot be ruled out, then dolutegravir and rilpivirine must be permanently discontinued and the Subject not rechallenged due to the risk of a recurrent reaction. If the liver event has a clear underlying alternative cause, other than drug-induced liver injury, then Drug Restart may be considered (see below).
- Report the event to the study sponsor pharmacovigilance team within 24 hours of learning its occurrence (see section 8.3)

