Suspected Unexpected Serious Adverse Reaction (SUSAR)	
A serious adverse reaction, the nature and severity of which is not consistent with the information about the medicinal product in question set out:
 
The reference safety information for the DTG/RPV FDC is contained within Juluca Summary of Product Characteristics (SmPC) at section 4.8 Undesirable effects, please refer to this document for further information on contraindicated treatments, drug interactions and adverse events expectedness.

“Severe” is often used to describe intensity of a specific event, which may be of relatively minor medical significance. “Seriousness” is the regulatory definition supplied above.

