8.2.2 Immunological evaluation

(f) Change from baseline in CD4, CD8, and CD4/CD8 ratio over 96 weeks with evaluation at week 24, 48, and 96.

The evolution of the CD4, CD8 and CD4/CD8 ratio over 96 weeks according to the treatment group will be described by boxplots for each treatment group at each visit. The changes will also be compared between the two treatment group using mixed models for repeated measures with random intercept and unstructured covariance matrix, adjusted for baseline value. The models will include treatment group, time, interaction between treatment group and time, and baseline value. Time will be considered as categorical variable (0, 12, 24, 48, 72 and 96 weeks) according the planned study visits. Visits window are shown in Table A (section 6.2). Data will be also summarised in tables by mean and standard error.

If the residual of the mixed model is not normally distributed and therefore does not allow the use of parametric test, the changes from baseline to week 24, 48 and 96 of CD4 T cell count, CD8 T cell count and CD4/CD8 ratio will be compared between the 2 groups using Mann-Whitney-Wilcoxon test.

9. Safety analyses:

(g) Number and percentage of participants with adverse events (AEs), severity of AEs, and treatment discontinuations due to AEs.

Adverse events (AE), especially grade 3 and 4 AE, serious adverse events (SAE), drug-related AE (all grades), treatment interruption due to AE (all grades), pregnancies and death will be summarized with descriptive statistics. The incidence rates of the events defined above will be compared between the treatment groups using a Poisson regression analysis which accounted for all adverse events and follow-up duration for each participant. The Poisson regression models will include the number of events, the treatment group and the duration of exposure in year in log. The number and percentage of death as well as the causes of death will be given. The number and percentage of pregnant women will also be given. A table will summarize the frequency of adverse events and pregnancies. This table will include the name of event, number and percentage of patients with events, number of events, and incidence rate (IR) per 100 person-years in the DTG/RPV group and the control group respectively, and incidence rate ratio (IRR) and 95%CI for IRR. All grades 3 or 4 AE related to the study drugs and treatment interruption due to AE will be put in the table.

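### SAP 9(g) compares drug-related AE rates between randomised groups with no cut at week 48, and Protocol 8.2.2 does not say which regimen counts as study drug for control before the switch

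*Protocol*

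**What the plan says.** **The comparison.** SAP section 9(g) covers grade 3 and 4 events, SAEs, "drug-related AE (all grades), treatment interruption due to AE (all grades), pregnancies and death will be summarized with descriptive statistics". The rates of these events are then compared between treatment groups by Poisson regression, with a rate ratio and 95% CI. The model counts all adverse events and uses each participant's follow-up as the time base. The section names no analysis period and no split at week 48. Protocol 7.1 and 7.5 and SAP 4.1 move the control arm to DTG/RPV at week 48.

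**The causality judgement.** Protocol 8.2.2 opens: "The relationship to study drug of each adverse event will be assessed using the following definitions". One of its categories reads "UNRELATED: the event occurs prior to dosing". Protocol 8.2 names a different object, the "causal relationship to the investigational product (unrelated, unlikely, possible, probable, and definite"). Neither says what this means for a control participant before week 48.

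**What counts as the product.** The header of the risk table in Protocol 1.1 is "Investigational Product (IP) [DTG/RPV FDC]". The SUSAR definition in 8.1 names one source for expectedness: "The reference safety information for the DTG/RPV FDC is contained within Juluca Summary of Product Characteristics (SmPC) at section 4.8 Undesirable effects". The liver procedure in 6.13 tells sites to "hold dolutegravir and rilpivirine". Against these, the synopsis row for the investigational product also lists "Boosted protease inhibitors or other ARV regimen (including Anatomical Therapeutic Chemical Classification System codes" follow). Section 7.1 covers the usual ARV regimen under the product heading, 7.2 gives pre-switch reference safety information by ATC code, and 7.4 covers the sourcing of boosted PIs and other combinations.

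**The concern.** There are two separate problems.

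First, a rate ratio by randomised arm over 96 weeks does not compare DTG/RPV with current ART. For half of that time both arms take DTG/RPV, and control events from that half are credited to control. This holds however *study drug* is read.

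Second, relatedness is an investigator's judgement in an open-label trial, and the text gives sites no rule for whose drugs are being judged in the control arm before the switch. If some sites judge against DTG/RPV only, the two arms are scored by different rules over the only period in which they take different regimens.

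The result at stake is the drug-related AE rate ratio, together with the grade 3 or 4 events related to study drugs that the same section tabulates.

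**Working it through.** The documents give no figure for drug-related AEs, so there is nothing to reproduce. What follows sets the texts side by side and then illustrates size. The event rates and the share of sites are assumptions.

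**1. Exposure by arm and period**

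| Period | Experimental arm | Control arm |
|---|---|---|
| Baseline to week 48 | DTG/RPV | current ART |
| Week 48 to 96 | DTG/RPV | DTG/RPV |

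The planned sizes are 100 and 50 (Protocol 9.1). With full follow-up, person-years to week 48 are 100 × 48/52.18 = 92.0 and 50 × 48/52.18 = 46.0. To week 96 they are 184.0 and 92.0, and 46.0 of the control 92.0 are on DTG/RPV.

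**2. Effect of having no cut, with both arms scored alike**

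Let d be the related-AE rate on DTG/RPV and c the rate on current ART, both constant over time, with R = d/c.

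- Ratio to week 48: d/c = R.
- Ratio over 96 weeks by randomised arm: d / [(c + d)/2] = 2d/(c + d) = 2R/(1 + R).

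For example, R = 1.5 becomes 3/2.5 = 1.20, and R = 0.5 becomes 1/1.5 = 0.67. A real difference in either direction is pulled towards 1.

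**3. Effect of the narrow reading (DTG/RPV only)**

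Suppose the true rates are equal, d = c = r, and a share s of control participants is at sites on the narrow reading, where control events before week 48 are all scored unrelated. The recorded control rate over 96 weeks is [(1 − s)r + r]/2 = r(1 − s/2).

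- s = 0: ratio 1.0.
- s = 0.5: r/(0.75r) = 1.33.
- s = 1: r/(0.5r) = 2.0. To week 48 alone the control count is 0, and the ratio is infinite or not estimable.

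**4. How often this would look like a finding (s = 1, equal true rates)**

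The exact conditional test of two Poisson rates stands in for the SAP's regression. Under equal rates the experimental share of events is 92.0/(92.0 + 46.0) = 2/3. Nine events against 0 is the smallest count that reaches p < 0.05 (p = 0.034). To week 48 the false-positive chance is therefore the Poisson probability of 9 or more experimental events.

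| Assumed rate per 100 person-years | Expected related events to week 48, experimental | Control, if judged against own drugs | Control, recorded | Chance of p < 0.05 at week 48 | Chance over 96 weeks |
|---|---|---|---|---|---|
| 5 | 4.6 | 2.3 | 0 | 4.5% | 10% |
| 10 | 9.2 | 4.6 | 0 | 57% | 23% |
| 20 | 18.4 | 9.2 | 0 | 99% | 46% |
| 30 | 27.6 | 13.8 | 0 | 100% | 66% |

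**5. Dependence on the time base**

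SAP 9(g) mentions both follow-up duration and duration of exposure. The 2.0 and 1.33 assume follow-up time. Counting only DTG/RPV exposure for control would remove the 2.0, but the control rate would then come wholly from after the switch and would no longer be a concurrent randomised comparison.

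**The case against.** A reader might infer that control participants cannot have a drug-related AE before week 48, because they are undosed and 8.2.2 makes events before dosing unrelated. The documents do not support that as a result.

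- The synopsis and Protocol 7.1, 7.2 and 7.4 place current ART under the investigational product or give it reference safety information. Pre-switch expectedness in 7.2 would have little purpose if pre-switch events could not be related.
- Protocol 6.12 has sites evaluate possible abacavir hypersensitivity in the current-ART arm. The serious adverse reaction definition in 8.1 refers to trial treatments in the plural.
- SAP 6.3.1 and 6.3.4 require receipt of study treatment in both arms. On the narrow reading, a control participant who left before week 48 would drop out of both populations.
- AEs are collected from consent (Protocol 8.2.3), so the dosing clause naturally covers the interval from consent to baseline.
- Inclusion criterion 10 admits people already taking DTG or RPV, so even the narrow reading is strict only if it means the fixed-dose tablet.

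The sizes can also be challenged. Equal true rates are doubtful when control is stable on its regimen for more than 24 weeks and the other arm starts new drugs. The half-and-half site split has no basis in the documents. The eCRF is not available and may ask about causality by regimen. Relatedness is also not part of the endpoint wording in Protocol 2.3.2 or SAP 3.2.2(g); it enters only in the analysis text.

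All of this stands. It reduces the causality issue to an ambiguity that the wider reading would resolve if it were written down. It does not touch the missing cut at week 48.

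**Conclusion.** The point holds in two parts of different strength.

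The missing cut is a defect on any reading. As written, the 96-week ratio mixes current-ART and DTG/RPV events in the control arm. With constant rates and equal scoring it moves R to 2R/(1 + R). The same model serves the other event types in 9(g), so their 96-week ratios are mixed in the same way.

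The undefined study drug is an unresolved ambiguity. The risk-table header and the SUSAR text lean towards DTG/RPV only, while the synopsis, 7.1, 7.2 and 7.4 include current ART. Where a site takes the narrow reading, control scores few or no related events before week 48, and the bias runs against DTG/RPV. The ratios of 2.0 and 1.33 and the false-positive chances are illustrations under assumed equal rates, assumed event rates and an assumed share of sites. They do not predict what the trial will show. This second part affects only rows that depend on causality; all-cause AEs, SAEs and deaths are not scored by it.

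The change should be made: it costs little and it alters a reported ratio.

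**What to change.** - **SAP 9(g).** Restrict the between-arm comparison of drug-related AEs to baseline to week 48, with person-time cut at the control switch. Report control events after the switch separately, as DTG/RPV exposure. State one time base.
- **Protocol 8.2.2, and the eCRF if it does not already do so.** State that relatedness is judged against the regimen taken at onset: current ART in control before the switch, DTG/RPV afterwards. State that the dosing clause means before randomised treatment starts at baseline. Reconcile the synopsis, the risk-table header in 1.1, 7.2, 8.1 and 8.2 with this.
- **Events already collected without this definition.** Describe related AEs on DTG/RPV only, and make the between-arm comparison on all-cause AEs.

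The cost is wording in both documents and causality queries for some control events. No new assessments are needed.

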8.2.3 Collection and follow up of Adverse Events

All adverse events, however minor, will be documented in the CRF whether or not the Investigator considers the event to be treatment related.

The adverse event reporting period will be from consent until the subject's final study visit (i.e. follow-up visit or end of trial visit). In addition, any untoward event that may occur subsequent to the reporting period that the Investigator assesses as possibly, probably or definitely related to the study drug medication should also be reported as an Adverse Event.

CONFIDENTIAL

Adverse events may be directly observed, reported spontaneously by the subject or by questioning the subject at each study visit.

All adverse events should be followed up until they are resolved or the subject's participation in the study ends (i.e. until the final CRF is completed for that subject). In addition, all serious and non-serious adverse events assessed by the Investigator as possibly related to the investigational medication should continue to be followed until resolution, or until no further change can reasonably be expected.

Rash and any associated symptoms should be reported as adverse events (see section 6.12)

8.2.4 Serious Adverse Events (SAE) & reportable events

See SAE definition within section 8.1.

Liver stopping criteria & clinically significant liver chemistry evaluation adverse events.

All AEs meeting liver stopping criteria, clinically significant liver chemistry elevations (as defined in section 6.13) associated with dolutegravir and all events of possible drug-induced liver injury (DILI) with hyperbilirubinemia defined as ALT \geq 3X_{ULN} and bilirubin \geq 2X_{ULN} (>35% direct) are considered serious for the purposes of this clinical trial and must be reported. See section 8.4 for reporting guidelines. NOTE: bilirubin fractionation should be performed if testing is available. If testing is unavailable, record presence of detectable urinary bilirubin on dipstick indicating direct bilirubin elevations and suggesting liver injury. If testing is unavailable and a subject meets the criterion of total bilirubin \geq 2X_{ULN}, then the event should still be reported as an SAE. If INR is obtained, include values on the SAE form. INR elevations >1.5 suggest severe liver injury.

Suicidality-related adverse event

If any subject experiences a possible suicidality-related adverse event (PSRAE) while participating in this study that is considered by the Investigator to meet above described definitions, this should be reported to the Sponsor. See section 8.4 for reporting format & timeline. A PSRAE may include, but is not limited to, an event that involves suicidal ideation, a preparatory act toward imminent suicidal behaviour, a suicide attempt, or a completed suicide. The investigator should exercise his or her medical and scientific judgment in deciding whether an event is possibly suicide related.

CONFIDENTIAL

Pregnancy

There is no requirement to report pregnancies in female partners of male participants. Please see risk section 1.1 for further details.

Trial subject pregnancies should be reported as per table 2

Overdose

All participants should be counselled about the importance of taking the medications as prescribed and they should understand the quantity of medicine they should be taking. Participants must be told to contact the clinic immediately if they take too much medication. If the overdose fits the criteria of an SAE (see Section 8) it should be reported appropriately. See table 2 for SAE reporting format and timelines.

Deaths

Any AE, adverse reaction or unexpected adverse reaction that results in death should be reported as an SAE. See table 2 for SAE reporting format and timelines.

Deaths occurring more than 28 days after the final dose, which are considered to be unrelated to the study medication, should not be reported as a Serious Adverse Event.

